## 6.4.2 Physical Examination

Physical exam data will be listed for the safety population. The listing will include exam date, body system, and result.

## 6.4.3 Vital Signs

The following vital sign test results and changes from baseline will be descriptively summarized by study visit for the safety population. Summaries will be displayed by treatment group and overall.

- Temperature (°F)
- Systolic and diastolic blood pressure (mmHg)
- Heart Rate (beats/minute)

A listing of the vital signs and weight for each study visit will be presented.

#### 6.4.4 Electrocardiogram

An electrocardiogram (ECG) is performed at screening. A listing of ECG date, parameters and interpretation will be provided for each subject in the ITT population.

#### 6.4.5 Laboratory Parameters

Laboratory data (Section 9.2) will be displayed by treatment group and overall for the safety population. Continuous data for laboratory tests of serum chemistry, hematology, urinalysis, and serum hormone including change from baseline will be descriptively summarized at each visit, and urinalysis categorical data will be summarized by visit. The number of subjects who have values outside the normal range will also be displayed descriptively at each time point.

A listing of serum chemistry, hematology, urinalysis, and serum hormone test results will be presented separately by visit. The numeric values will be flagged/indicated with LN = Low Normal, LP = Low Panic, N = Normal, HN = High Normal, HP = High Panic in the listing.

#### 6.5 PK Analysis

Samples of venous blood for the determination of trough plasma concentrations of VERU-944 will be collected on Days 1 (prior to dose), 30, 60, and 84. VERU-944 trough concentrations will be determined in each subject and summarized by mean, median, standard deviation, and coefficient of variation, maximum, and minimum for each treatment arm.

#### 6.6 Caprini VTE Risk Assessment

The VTE risk assessment data will be summarized for the safety population at each visit, by treatment group and overall.

#### 6.7 Interim Analysis

During Stage 1, after the last subject has completed the Day 42 visit, an unblinded interim analysis (IA) of the Week 6 (Day 42) hot flash primary endpoint (frequency) and first secondary endpoint (severity) of VERU-944 will be conducted. A blinded analysis of the safety will also be conducted. Both the Sponsor and CRO study team will remain blinded to patient level data until completion of the study stage. An

unblinded statistical support group, independent of the study team (within the CRO), along with a representative of Veru Inc., will review the IA results and determine steps forward. It is of note that due to the material nature of the IA results of this study in the business of Veru Inc., a publicly traded company, these results may be required to be released in a press release prior to the completion of Stage 1 of this study.

The analyses to be included in the IA will be the analyses of hot flash frequency at Week 6 (Section 6.3.1.1) and the hot flash severity at Week 6. These analyses will include the summary statistics and MMRM model for both the ITT and EEIA populations. The sensitivity analyses associated with these sections will not be conducted during the IA.

In addition to the efficacy analyses, a blinded safety report will be reviewed to assess drug safety. All IA analyses will be conducted on the EEIA population.

If an effective dose of VERU-944 is achieved in Stage 1, as defined as a statistically significant result), the Sponsor reserves the right to not initiate Stage 2 of the protocol. However, if an effective dose is not achieved in the Stage 1 IA, then the study will commence with Stage 2.

Regardless of IA outcome, unless safety issues are observed, the Stage 1 section of the study will continue to completion at 12 Weeks with Follow-up.

Assuming Stage 2 is implemented, an additional replicate IA will be conducted after the last subject in Stage 2 has completed the Day 42 visit. This IA will follow the same procedures as done for Stage 1.

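### SAP 6.7, on the move to 100 mg, read literally puts interim safety on the wrong population and omits the protocol's safety condition; no by-arm safety comparison is required first

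*SAP*

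**What the plan says.** Protocol 7.2.3 allows 100 mg only if 50 mg has proved ineffective and the Stage 1 side effects, judged blinded, are acceptable. Protocol 2.0 (Stage 2 dosing evaluation) lets the sponsor withhold Stage 2 if the Stage 1 safety profile is unacceptable. SAP 3 says that the interim assesses efficacy unblinded and safety blinded, and that the Stage 2 decision follows review of the Stage 1 results.

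SAP 6.7 holds the operating rules:

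- An unblinded CRO statistical group, "along with a representative of Veru Inc., will review the IA results and determine steps forward". The listed analyses are Week 6 frequency and severity, "for both the ITT and EEIA populations".
- On safety: "In addition to the efficacy analyses, a blinded safety report will be reviewed to assess drug safety". The sentence directly after it reads: "All IA analyses will be conducted on the EEIA population".
- On starting Stage 2: "However, if an effective dose is not achieved in the Stage 1 IA, then the study will commence with Stage 2".
- On blinding: "Both the Sponsor and CRO study team will remain blinded to patient level data until completion of the study stage". Unless safety issues arise, "the Stage 1 section of the study will continue to completion at 12 Weeks with Follow-up".

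Protocol 9.2 and SAP 5 define the Safety population as everyone who received at least one dose and say that the safety analyses use it. EEIA requires analyzable baseline data, six weeks of hot flash data, at least 80% drug compliance and no major deviation.

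**The concern.** Two sentences in SAP 6.7 give the wrong result if followed as written. The EEIA sentence would remove from the interim safety report the men most likely to have had a problem: those who stopped early. The Stage 2 sentence makes lack of efficacy sufficient to begin 100 mg, whereas the protocol also asks for acceptable safety.

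The third issue is one of design. Whether toxicity rises from 10 mg to 50 mg is the most direct Stage 1 evidence for judging 100 mg. Without a by-arm view, an excess at 50 mg might not be recognised as such, or Stage 2 might be withheld because of events on placebo. Liver tests are a relevant example: Protocol 7.2.3 reports liver test elevations, weight loss and death in dogs at a human-equivalent 667 mg/day, which is 667/50 = 13.3 times the 50 mg dose and 667/100 = 6.7 times the 100 mg dose. Those at stake are the men who would enter Stage 2. The primary efficacy analysis is not affected.

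**Working it through.** The plan gives no figure of its own to reproduce here. The first two points come from setting texts side by side; the rest is arithmetic on stated inputs, with assumptions marked.

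**1. Who drops out under EEIA.**
- Diary: a week counts only with at least 4 recorded days, and Week 6 is Days 36 to 42 (SAP 6.3.1). The earliest day on which 4 such days can exist is Day 39. A man whose diary ends by Day 38 has at most 3 (Days 36, 37, 38) and no Week 6 value. Protocol 8.11 discontinues men with Grade 3 or higher toxicity considered related to study drug, and Protocol 8.12 asks discontinued men to return the electronic device.
- Compliance: SAP 6.2.4.2 divides pills taken by pills expected but does not say over what period. Assume Days 1 to 42. By Protocol 7.3, capsules through Day d (from Day 4) are 5 + 3×3 + (d − 4) = d + 10, so 52 by Day 42, and 80% of 52 is 41.6. A last dose on Day 14 gives 24/52 = 46.2%, on Day 30 40/52 = 76.9%, on Day 31 41/52 = 78.8% and on Day 32 42/52 = 80.8%. A man stopped for liver tests at the nominal Day 14 or Day 30 visit would therefore fail. If expected pills are counted only to the stop date, this route does not exclude him, but the diary route still can.

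**2. The condition for Stage 2.** Protocol 7.2.3: 50 mg ineffective and safety acceptable. Protocol 2.0: right to withhold for safety. SAP 3: blinded safety is an interim input, then a decision. SAP 6.7: no effective dose, so Stage 2 commences. Only the last omits safety.

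**3. Is a by-arm comparison required first?** Protocol 2.0 and 7.2.3 and SAP 3 and 6.7 all make interim safety blinded. By-arm safety tables are planned (SAP 6.4.1, 6.4.5, 7.1), but nothing makes Stage 2 wait for them. The individual stopping rules (Protocol 8.11), the code break (Protocol 7.1) and the Safety Review Team (Protocol 9.3.4.1, SAP 6.8) are not stated to compare arms.

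**4. Timing.** Nominal follow-up is Day 84 + 30 = Day 114, so it lies 114 − 42 = 72 days after Day 42. Assume that Stage 2 screening begins at the decision, x days after the last Stage 1 Day 42. Fourteen diary days (Protocol 8.2) plus at least 2 days from enrollment to Day 1 (Protocol 8.3) put the first 100 mg dose at x + 16 or later.
- It can precede the last Stage 1 Day 84 if 42 + x + 16 < 84, so x < 26.
- It can precede the last follow-up if 42 + x + 16 < 114, so x < 56.

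**5. What by-arm tables could show.** One-sided Fisher test at 0.10, with assumed rates:

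| Per arm | 30% vs 10% | 20% vs 10% |
|---|---|---|
| 30 | 0.65 | 0.30 |
| 40 (maximum) | 0.78 | 0.38 |

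Observed counts of 4/30 vs 0/30 give p = 0.056, and 3/30 vs 0/30 give p = 0.119.

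**6. If the blinded report is pooled** (its format is not stated). With equal arms, an excess at 50 mg is diluted by 3/(1 + r), where r is the 10 mg excess as a share of the 50 mg excess: 3.0-fold at r = 0 and 1.5-fold at r = 1. Nine events in 90 look the same whether split 3/3/3 over placebo, 10 mg and 50 mg (50 mg vs placebo p = 0.66) or 0/0/9 (p = 0.001).

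**The case against.** The strongest reply is that blinded safety review was chosen deliberately and stated consistently. It protects adverse event grading and causality assessment while Stage 1 runs on to Day 84 and follow-up. That stands: wanting by-arm tables is a judgement about design, and no text is contradicted.

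A reader might infer that Stage 2 could start with no safety review at all. The documents do not support that. Protocol 7.2.3 and 2.0 keep safety in the decision, SAP 3 names it as an interim input, and SAP 6.9 declares no change from the protocol's methods. The gap is in the SAP 6.7 sentence, which should match them.

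The EEIA sentence may have been meant for efficacy only. It already disagrees with the ITT and EEIA wording in the paragraph before it, so its scope is unsettled, and its position makes safety the natural literal reading.

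Liver risk has protection that does not depend on arm: entry limits on ALT and AST (Protocol 6.2.2), chemistry at Days 14, 30, 60 and 84, and fixed stopping limits (Protocol 8.11). These protect individual men. They do not show whether risk rises with dose.

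Finally, all event rates above are assumed, the plan specifies no safety test, and 0.10 is borrowed from efficacy. The power figures show only how coarse a by-arm look would be.

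**Conclusion.** Two sentences in SAP 6.7 need correcting. Followed literally, one takes early stops out of the interim safety report, contrary to the Safety population rule in Protocol 9.2 and SAP 5. The other drops the safety condition for 100 mg. Both are wording faults.

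The absence of a required by-arm safety comparison is a smaller point and a design weakness. Under Protocol 7.2.3 it matters only if 50 mg is not effective, and with 30 men per arm it would reveal mainly large differences. It is worth fixing because a CRO group and a sponsor representative already see efficacy by arm and determine the next steps.

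A reader might go further and infer that 100 mg would necessarily be given before any by-arm Stage 1 safety data existed. The documents do not show that: the tables are planned, and the order depends on how fast the decision comes (under 26 or 56 days in the timing above, on the screening assumption). Nor do they say that the blinded report is pooled; masked arm codes are possible, though these would still not identify the 50 mg arm.

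**What to change.** **1. Now, in SAP 6.7 only.** Limit the EEIA sentence to the efficacy analyses and reconcile it with the ITT and EEIA paragraph. State that the interim safety report uses the Safety population. Make the start of Stage 2 conditional on both no effective dose and an acceptable Stage 1 safety profile, and retain the sponsor's right to withhold it, as in Protocol 7.2.3 and 2.0. The cost is SAP wording.

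**2. Recommended at the next amendment, in SAP 3 and 6.7 and Protocol 2.0 and 7.2.3 together.** SAP 3 must be included, or it would then contradict SAP 6.7. Before Stage 2 starts, the existing unblinded CRO group prepares aggregate safety tables by arm for the decision-makers who are already unblinded: adverse events by grade, serious events, thromboembolic events, discontinuations and liver tests. Sites, patients, the Medical Monitor and the study team stay blinded.

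Part 2 adds no patients and spends no efficacy alpha; most of the tables are already specified by treatment group. Its costs are real, however. It probably needs IRB/IEC approval as a substantial amendment (Protocol 10.3). A rare event could reveal one man's treatment. By-arm safety would join an interim package of which SAP 6.7 says "these results may be required to be released in a press release prior to the completion of Stage 1 of this study". If a medically qualified sponsor representative with no Stage 1 role is wanted, a different person may have to be unblinded.

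### SAP 6.7 contradicts itself on the interim efficacy population, leaves the population of the blinded safety report unclear, and starts Stage 2 without the protocol's side-effect precondition

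*SAP*

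**What the plan says.** SAP 6.7 sets out an unblinded interim efficacy analysis and a blinded safety review once the last Stage 1 subject completes Day 42.

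- **Content.** "The analyses to be included in the IA will be the analyses of hot flash frequency at Week 6", together with severity at Week 6. Summary statistics and the MMRM are to be produced "for both the ITT and EEIA populations". "The sensitivity analyses associated with these sections will not be conducted during the IA".
- **Safety and population.** The next paragraph adds the safety report and then a general population statement: "a blinded safety report will be reviewed to assess drug safety. All IA analyses will be conducted on the EEIA population".
- **Stage 2.** If a dose is statistically significant, the sponsor may choose not to start Stage 2. "However, if an effective dose is not achieved in the Stage 1 IA, then the study will commence with Stage 2".
- **Stage 1.** "Regardless of IA outcome, unless safety issues are observed, the Stage 1 section of the study will continue to completion".
- **Who decides.** An unblinded statistical group within the CRO, with a sponsor representative, "will review the IA results and determine steps forward".
- **Second interim.** If Stage 2 runs, it has its own interim: "This IA will follow the same procedures as done for Stage 1".

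**The concern.** Three things in SAP 6.7 do not fit together or do not fit the protocol.

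1. **Safety report population (an ambiguity).** The EEIA sentence directly follows the safety report and covers every interim analysis. EEIA requires six weeks of diary data, at least 80% compliance and no major deviations. A safety report on that set would leave out men who left early, some of them because of toxicity.
2. **Efficacy population (a direct contradiction).** ITT is included in one paragraph and excluded in the next. A programmer cannot tell whether to run it at an unblinded look whose results, SAP 6.7 notes, may have to be released publicly before Stage 1 ends.
3. **Stage 2 start (SAP against protocol).** The start sentence depends on efficacy alone. Protocol 7.2.3 adds a side-effect precondition, introduced after dose-limiting toxicity was seen in dogs at a high dose.

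This interim is the input to the decision on the 100 mg stage, and its procedures are reused for the interim in the 100 mg stage itself.

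**Working it through.** The plan gives no figure to reproduce on this point. The check sets the texts side by side, then works out who falls outside EEIA.

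**Step 1. Efficacy population**

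| Source | Content |
|---|---|
| SAP 6.7, content paragraph | ITT and EEIA at the interim |
| SAP 6.7, next paragraph | EEIA for all interim analyses |
| SAP 6.3.1 | EEIA is the population of interest at Week 6; ITT is for sensitivity analyses |
| SAP 6.3.1.1.2 | ITT analyses are sensitivity analyses |
| SAP 6.7 | Sensitivity analyses are not run at the interim |

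Rows 1 and 2 contradict each other. Rows 3 to 5 together imply no ITT at the interim, which contradicts row 1 again.

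**Step 2. Safety population**

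- SAP 3 describes the interim analysis as assessing both unblinded efficacy and blinded safety, so safety is one of its components.
- SAP 6.7 then puts all interim analyses on EEIA.
- SAP 5 and Protocol 9.2 put safety analyses on everyone who took at least one dose.

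Read literally, the first two conflict with the third.

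**Step 3. Who a literal EEIA safety report could omit**

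*Diary criterion.* Assumption: six weeks of hot flash data requires a non-missing Week 6. Week 6 is Days 36 to 42 (SAP 6.3.1, Data Handling), and a week needs at least 4 recorded days (SAP 6.1.2).

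- Recording ends on Day 38: Days 36, 37, 38 = 3 days at most, so Week 6 is missing and the man is outside EEIA.
- Recording ends on Day 39: Days 36 to 39 = 4 days, so Week 6 can be non-missing.

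Protocol 8.11 takes men with related Grade 3 or greater toxicity off the study, and Protocol 8.12 asks men who are discontinued to return the electronic device. If that happens before about Week 6, they fail this criterion. The liver-enzyme rule in Protocol 8.11 stops dosing only, so those men may keep recording. Men who leave after their own Day 42 may also remain in EEIA.

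*Capsule criterion.* Protocol 7.3 gives 5 capsules on Day 1, 3 on each of Days 2 to 4, and 1 a day from Day 5.

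- Due through Day 42: 5 + 3×3 + 38 = 52.
- Taken by a fully adherent man whose last dose is Day 21: 5 + 9 + 17 = 31.
- Compliance: 31/52 = 59.6% if the denominator runs to Day 42, or 31/31 = 100% if it stops with him.

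SAP 6.2.4.2 does not define the expected count, so this criterion gives no fixed cut-off. The third criterion, no major deviations, could remove further men and cannot be quantified.

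*Number of men.* The documents give no rate of toxicity departures, so no expected number of omitted men follows.

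**Step 4. Start of Stage 2**

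| Source | Rule |
|---|---|
| SAP 6.7 | Starts if no effective dose is found; no safety condition |
| Protocol 7.2.3 | 100 mg not used unless 50 mg is shown not effective and the Stage 1 side-effect profile is acceptable |
| Protocol 2.0 | Stage 2 is optional; sponsor reserves the right not to start it if safety is unacceptable |
| SAP 3 | Decision taken after review of Stage 1 results |
| SAP 6.9 | No change from the protocol's methods |

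SAP 6.7 is the only one worded as automatic. Its own next paragraph has a safety exception, but only for completing Stage 1. The efficacy trigger also differs: Protocol 7.2.3 turns on 50 mg, SAP 6.7 on any Stage 1 dose. The protocol is not uniform either, since 7.2.3 states a precondition and 2.0 a reserved right.

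**The case against.** The strongest reply concerns the safety report. SAP 6.7 defines the interim content as Week 6 frequency and severity and presents the safety report as something additional. EEIA is by name an efficacy population. SAP 5, Protocol 9.2 and the SAP's adverse event, vital sign, laboratory and Caprini sections all use the Safety population. The EEIA sentence was therefore probably meant for efficacy only. Early leavers' events would also not go unseen, because the Safety Review Team reviews all SAEs at least monthly without any EEIA restriction (SAP 6.8, Protocol 9.3.4.1).

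This stands as to likely intent and lowers the risk. It does not remove the ambiguity, since SAP 3 counts blinded safety within the interim analysis and the sentence says all. The point is therefore held with moderate confidence.

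On efficacy, SAP 6.3.1 already makes EEIA the Week 6 population of interest, so the ranking is clear and only the supporting ITT run is in doubt. That is fair, and this part is minor in consequence, but the contradiction is plain.

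On Stage 2, the same section has a safety report reviewed and gives those reviewing the results discretion over next steps. SAP 3 calls for a decision, and SAP 6.9 suggests the SAP is to be read subject to the protocol. A careful sponsor would probably not start 100 mg on efficacy alone. The sentence still reads as automatic, omits a condition the protocol states, and sits beside a safety exception written for Stage 1 only. With no formal data monitoring committee (SAP 6.8), the written rule carries more weight.

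**Conclusion.** The concern holds; it should be fixed. The efficacy contradiction and the Stage 2 mismatch are held with high confidence and rest on the text alone. The safety-report point is held with moderate confidence: it is an ambiguity whose literal reading conflicts with SAP 5 and Protocol 9.2.

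The consequence is qualitative. Followed literally, SAP 6.7 would start the 100 mg stage on efficacy alone and would base the interim safety report on a set that excludes men whose diaries end by Day 38. The Day 38 boundary assumes that EEIA requires a non-missing Week 6. Ongoing review by the Safety Review Team reduces the practical risk but does not correct the text. The wording also carries over to the Stage 2 interim.

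**What to change.** In SAP 6.7:

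1. State that the blinded interim safety report uses the Safety population, meaning all dosed subjects.
2. Limit the EEIA sentence to the efficacy analyses, and say whether ITT is run at the interim.
3. Reconcile the Stage 2 start sentence with Protocol 2.0, Protocol 7.2.3 and SAP 3, including whether the efficacy trigger is 50 mg or any Stage 1 dose. Which rule is right is for the sponsor to settle; none is proposed here.

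Items 1 and 2 cost only SAP wording: no unblinding, no new output and no change to the EE/EEIA primary population. Reasons for discontinuation are already tabulated under SAP 6.2.1. Item 3 is SAP wording if the protocol text stands, or a protocol amendment if it does not. Because the Stage 2 interim follows the same procedures, the corrections to the population wording carry over to it.

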### **8.11 Subject Stopping Rules**

If, in the opinion of the investigator, the participation in the study is or is becoming detrimental to the well-being of a particular subject, this issue should be discussed with the Medical Monitor for this study and dosing may be discontinued.

Subjects that experience a Grade 3 or greater toxicity according to the Common Terminology Criteria for Adverse Events (CTCAE) version 4

([https://evs.nci.nih.gov/ftp1/CTCAE/CTCAE\\_4.03\\_2010-06-14\\_QuickReference\\_5x7.pdf](https://evs.nci.nih.gov/ftp1/CTCAE/CTCAE_4.03_2010-06-14_QuickReference_5x7.pdf)) that is deemed to be possible, probably or definitely related to study drug will be discontinued from the study. Prior to discontinuation from the study, the grading of the event and causal relationship should be discussed with the Medical Monitor for the study.

Subjects will be discontinued from dosing if AST or ALT levels are >5 times the upper limit of normal, or if AST or ALT levels are >3 times the upper limit of normal along with a total bilirubin elevation of >2 times the upper limit of normal.

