### **8.12 Early Discontinuation of Study Treatment**

A subject will be considered to have completed the trial if they received at least 84 days of treatment with VERU-944 or the study is terminated by the sponsor. Subjects may prematurely discontinue study treatment for any of the following reasons:

1. Consent Withdrawn (specify the reason).
2. Significant and unacceptable adverse event – specify the adverse event leading to discontinuation
3. Investigator decision (specify the reason), must be approved by the Medical Monitor
4. Non-compliance by subject with protocol requirements, must be approved by the Medical Monitor
5. Lost to follow-up (record the date of last contact)
6. Death (specify the following information)
  - a. Date of death
  - b. Death due to primary disease? Yes or no
  - c. Death due to study drug? Yes or no
  - d. Death due to adverse event? Yes or no
7. Study terminated by the Sponsor
8. Other reason (specify the reason) should be approved by the Medical Monitor

The reason for discontinuation of study treatment will be documented for each subject. Subjects who discontinue prematurely will not be replaced. If a subject is discontinued from the study, he will be asked to complete all End of Study visit assessments and return all study materials (study medication and electronic device). At the time of discontinuation, please fill out the End of Study case report forms (eCRFs) and subject disposition eCRF pages.

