### **9.2 Populations**

**Intent-to-Treat (ITT) population:** All enrolled subjects who have taken at least one dose of study drug.

**Efficacy Evaluable (EE) population:** All subjects in the ITT population who have analyzable baseline data and 12 weeks of hot flash data. Subjects must also be at least 80% compliant with taking study drug with no major protocol deviations, including no major inclusion/exclusion deviations.

**Efficacy Evaluable Interim Analysis (EEIA) population:** All subjects in the ITT population who have analyzable baseline data and 6 weeks of hot flash data. Subjects must also be at least 80% compliant with taking study drug with no major protocol deviations, including no major inclusion/exclusion deviations.

**Safety population:** All subjects that receive at least one dose of study medication. The safety analyses will be conducted on this population.

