# 3. STUDY DESIGN

This is a randomized, multicenter, double-blind, placebo-controlled dose finding study of VERU-944 to treat hot flashes (vasomotor symptoms) in men with advanced prostate cancer on ADT. The study will be conducted as a staged study with Stage 1 consisting of 3 arms (placebo, 10 mg and 50 mg of VERU-944). When all subjects in Stage 1 have completed the Week 6 of dosing, an interim analysis will be conducted to assess efficacy (unblinded) and safety (blinded) of the doses administered in Stage 1 at Week 6 frequency and severity – with the Week 6 frequency analysis being the primary analyses. Following review of the Stage 1 results, a decision will be made whether to progress with Stage 2 of the study. If initiated, Stage 2 will have 2 arms (placebo and 100 mg VERU-944). It is important to note that the placebo arm of Stage 2 will be enrolled with separate and distinct subjects from those subjects who receive placebo in Stage 1. There is no intent to combine these placebo arms for analysis purposes of this protocol.

The subjects participating in the study will have advanced prostate cancer and will be undergoing ADT with a luteinizing hormone releasing hormone therapy (agonist or antagonist) for at least 3 months prior to randomization and be experiencing regular moderate to severe hot flashes while on ADT. Subjects will continue to receive ADT over the course of the study.

Approximately 30 subjects will be enrolled into each arm, regardless of stage of study. Each subject will be randomized to receive placebo, 10 mg VERU-944, or 50 mg VERU-944 in Stage 1, and placebo, or 100 mg VERU-944 in Stage 2. Following randomization, each subject will receive a 4-day loading dose of the treatment to which they have been randomized. On Day 1, each subject will receive 5 times their maintenance dose at a single time. On Days 2-4 each subject will receive 3 times their maintenance dose at a single time on Days 5-84, each subject will receive 1 capsule per day. Dosing should occur greater than 1 hour before or 1 hour after eating and will continue for 12 weeks (84 days).

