## 5. ANALYSIS POPULATIONS

The subjects will be over the age of 18 and will have moderate to severe hot flashes, defined as a minimum of 4 moderate to severe hot flashes per day or 12 per week at baseline. The 4populations are as follows:

Intent-to-Treat (ITT) population:	All enrolled subjects who have taken at least 1 dose of study drug.
Efficacy Evaluable (EE) population:	All subjects in the ITT population who have analyzable baseline data and 12 weeks of hot flash data. Subjects must also be at least 80% compliant with taking study drug with no major protocol deviations, including no major inclusion/exclusion deviations.

Efficacy Evaluable (EEIA) population for IA:	All subjects in the ITT population who have analyzable baseline data and 6 weeks of hot flash data. Subjects must also be at least 80% compliant with taking study drug with no major protocol deviations, including no major inclusion/exclusion deviations.
Safety population:	All subjects who receive at least 1 dose of study drug. The safety analyses will be conducted on this population. This population is the same as the ITT population.

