#### 6.1.2 Handling of Dropouts and Missing Data

Subjects must have entered hot flash data (frequency and severity) for 4 or more days in a given week for their data to be considered non-missing. No other imputation procedures will be used to impute missing data. If a subject enters that there are no hot flashes to report on a given day, then this will be considered a data point equal to zero. If a subject does not report any hot flash information across consecutive days,

the data management team will be alerted to query the situation. From a data perspective, if a subject fails to report hot flash information on a given day, then that day will be recorded as missing.

For determining whether adverse events (AEs) are treatment-emergent when the start date of the AE is a partial date, refer to Section 6.4.1.

For determining whether a medication is a prior medication or concomitant medication, refer to Section 6.2.5.

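### SAP 6.7 leaves the population for the interim blinded safety report in conflict: read literally it is EEIA, which would drop most men stopped for toxicity before about Week 6

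*SAP*

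**What the plan says.** **Scope of the interim analysis.** SAP 3 says that once Stage 1 has completed Week 6, "an interim analysis will be conducted to assess efficacy (unblinded) and safety (blinded) of the doses administered in Stage 1". SAP 6.7 repeats that a blinded safety analysis accompanies the unblinded hot flash analyses. It plans the interim efficacy models on two populations, ITT and EEIA. In a later paragraph it introduces the blinded safety report, and the next sentence reads "All IA analyses will be conducted on the EEIA population".

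**Populations.** SAP 5 defines the Safety population as "All subjects who receive at least 1 dose of study drug. The safety analyses will be conducted on this population". Protocol 9.2 says the same: "All subjects that receive at least one dose of study medication. The safety analyses will be conducted on this population". SAP 6.4 names the safety population for adverse events, vital signs and laboratory data. SAP 5 defines EEIA as "All subjects in the ITT population who have analyzable baseline data and 6 weeks of hot flash data", and adds at least 80% drug compliance and no major deviations. SAP 6.9 declares no departure from the protocol's methods.

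**Stopping rules.** Protocol 8.11 includes a liver rule: "Subjects will be discontinued from dosing if AST or ALT levels are >5 times the upper limit of normal", or above 3 times that limit together with total bilirubin above 2 times its limit. Under the same section, a Grade 3 or greater toxicity judged related takes the man out of the study. Under protocol 8.12, when a man leaves the study early, "he will be asked to complete all End of Study visit assessments and return all study materials (study medication and electronic device").

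**The concern.** EEIA is an efficacy set that selects on having stayed on drug and kept the diary for six weeks. A man whose toxicity ended his dosing in the first weeks will usually fail one or both conditions. If the safety report is run on EEIA, it leaves out the men who say most about tolerability.

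The report has a purpose. Protocol 7.2.3 allows 100 mg only if 50 mg is not effective and the blinded Stage 1 side effect profile is acceptable, and the protocol summary lets the sponsor withhold Stage 2 on safety grounds. There is no formal data monitoring committee (protocol 9.3.4.1, SAP 6.8). SAP 6.7 also has the Stage 2 interim analysis follow the same procedures, so the wording would carry over to the 100 mg arm.

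**Working it through.** The plan gives no figure to reproduce. The check is which men would leave EEIA.

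**1. Diary condition.** SAP 6.3.1 defines Week 6 as Days 36 to 42. For a week to count, "Subjects must have entered hot flash data (frequency and severity) for 4 or more days in a given week" (SAP 6.1.2). I take six weeks of data to require a non-missing Week 6.
- Diary ends Day 38: Days 36–38 = 3 days, so Week 6 is missing.
- Diary ends Day 39: Days 36–39 = 4 days, so Week 6 counts.

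A diary that ends before Day 39 therefore fails EEIA. The scheduled chemistry draws before Day 42 are Day 14 (±3, so Days 11–17) and Day 30 (±7, so Days 23–37). A man who stops and returns the device at either draw has no Week 6.

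**2. Compliance condition, for a man who keeps the diary.** SAP 6.2.4.2 defines compliance as capsules taken divided by capsules expected, times 100. Protocol 7.3 gives 5 capsules on Day 1, 3 per day on Days 2–4 and 1 per day from Day 5. Assume expected capsules run to Day 42.
- Expected: 5 + 3×3 + 38 = 52.
- Taken by a man whose last dose is Day d (d ≥ 5): 5 + 9 + (d − 4) = d + 10.

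| Last dose | Taken | Compliance | Meets 80%? |
|---|---|---|---|
| Day 14 | 24 | 24/52 = 46% | No |
| Day 30 | 40 | 40/52 = 77% | No |
| Day 31 | 41 | 41/52 = 79% | No |
| Day 32 | 42 | 42/52 = 81% | Yes |

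A last dose before Day 32 fails on compliance alone.

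**3. Who stays in.** A man stopped early remains in EEIA only if he keeps the diary to at least Day 39 and either his last dose is Day 32 or later, or expected capsules are counted only to his own stop date. The SAP does not define the expected count for early stoppers.

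**4. Illustration.** Assume 90 men (30 per arm), no other exclusions, and 6 of 30 stopped at 50 mg by Day 30 with diaries returned.
- Safety population, pooled: 6/90 = 6.7%.
- EEIA, pooled: 90 − 6 = 84 men, so 0/84.
- One-sided 95% upper limit for 0/84: 1 − 0.05^(1/84) = 3.5%, below the actual 6.7%.

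**5. The efficacy-only reading.** If the sentence covers efficacy alone, it restricts interim efficacy to EEIA. The earlier paragraph of 6.7 runs the same summaries and models on ITT as well. The two statements cannot both hold.

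**The case against.** The best defence is that 6.7 introduces the abbreviation IA for the two hot flash endpoints, mentions safety in a separate sentence, and lists only the frequency and severity analyses as the IA's contents. On that view the safety report sits beside the IA, and the general rules in SAP 5, SAP 6.4 and protocol 9.2 govern it. SAP 6.9 fits this reading too. The table specifications, which are not in the documents, may already name the right population.

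Much of this stands. A reader might infer that the plan has settled on EEIA for interim safety. The documents do not support that: they contain a specific sentence and several general rules that disagree, and nothing says which prevails. But the defence does not rescue the sentence, because SAP 3 places blinded safety inside the interim analysis and the efficacy-only reading fails at step 5.

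A reader might also infer that these men would be hidden from the sponsor. They would not be. Grading and causality of related Grade 3 or greater events are to be discussed with the Medical Monitor before the man is discontinued from the study (protocol 8.11). Serious events are reported within 24 hours, and the Safety Review Team meets at least monthly.

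A third inference is that an empty EEIA report would mask a 10% stop rate at 50 mg. With 3 of 30 stopped, the pooled Safety rate is 3/90 = 3.3%, and the upper limit for 0/87 is 1 − 0.05^(1/87) = 3.4%, which still covers it. The gap between 3.3% and 10% comes from blinded pooling, which would remain under the corrected wording.

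**Conclusion.** The population for the interim safety report is in conflict, and the sentence is wrong on either reading. Followed literally, it would drop most men stopped under protocol 8.11 before about Week 6, by the Day 39 diary cut-off or the Day 32 dosing cut-off. In the illustration that turns 6/90 into 0/84.

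The cut-offs rest on three assumptions: Week 6 must be non-missing for EEIA; expected capsules run to Day 42; and, for the diary route, the device is returned at the stop. The last is not certain for liver stops. The liver rule ends dosing, while device return in protocol 8.12 is tied to leaving the study. The stop counts are hypothetical. The documents give no expected rate, and the liver findings in dogs were at a human-equivalent dose of 667 mg, well above the 50 and 100 mg maintenance doses.

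The effect is limited to the interim report: ongoing safety review is separate, and the final safety tables use the Safety population. Confidence is medium, because the intended population may well have been the Safety population. The sentence should be corrected because this report informs the decision on 100 mg.

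**What to change.** In SAP 6.7, replace the sentence with:

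> IA efficacy analyses use the EEIA population, with ITT as stated above. The blinded safety report uses the Safety population, pooled across arms, with all data from first dose to the data cut-off, including men who have stopped drug or left the study.

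Apply the same wording to the Stage 2 replicate interim analysis, and check that the table specifications agree.

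The cost is two sentences and, if the safety program was set to EEIA, a change of population flag. SAP 5 makes the Safety and ITT populations identical, so the set is already defined for the interim analysis. No new data, visits or unblinding are needed.
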